7.2.6.1 Pharmacokinetic Endpoints

As far as feasible, the following pharmacokinetic parameters will be derived by noncompartmental methods:

- C_{max} Maximum concentration of ALK4290 in plasma after single dose
- t_{max} Time of C_{max} relative to last dosing
- $t_{max,ss}$ Time of $C_{max,ss}$ relative to last dosing
- $C_{pre,ss,N}$ Pre-dose concentration of ALK4290 in plasma immediately before administration of the Nth dose

In addition, the average pre-dose concentration in plasma at steady state will be calculated as the geometric mean of $C_{pre,ss,N}$ values.

7.2.6.2 Methods of Sample Collections

For quantification of ALK4290 plasma concentrations and for biomarker investigations (see [Section 7.2.8](#)), one blood sample of approximately 6 mL per sampling time point (see [Section 17.2.1, Table of Pharmacokinetic, Biomarker, and Pharmacogenomic Sampling](#)) will be taken from an antecubital or forearm vein into a potassium ethylenediaminetetraacetic acid (EDTA)-anticoagulant blood drawing tube.

[figure not shown]
The EDTA-anticoagulated blood samples will be centrifuged to collect plasma. For pharmacokinetic samples only, the obtained plasma will be split into 2 aliquots and stored in polypropylene tubes. At the selected time points with additional biomarker determinations, 5 instead of 2 aliquots of at least 0.5 mL plasma each will be prepared from the blood sample. The time from blood collection until the transfer of plasma aliquots into the freezer should not exceed 60 minutes, with interim sample storage on wet ice whenever possible. Samples will be positioned upright and will be frozen at approximately -20°C or below until shipment. These aliquots will be processed by the central laboratory. Details of plasma collection, sample handling, and shipment instructions will be provided in the Lab Manual/ISF.

7.2.6.3 Analytical Determinations

Concentrations of ALK4290 and metabolites (if feasible) in plasma samples will be determined by a validated high performance liquid chromatography, tandem mass spectrometry (HPLC-MS/MS) assay. Leftover samples will be used for exploratory biomarker assessment (see [Section 7.2.8](#)).

7.2.7 PHARMACOGENOMIC EVALUATIONS

Pharmacogenetic analysis of prespecified genes is mandatory and a prerequisite for participation in this study.

- [REDACTED]

Prespecified analyses will be performed at the end of the trial and the data will be part of the report. All remaining samples will be destroyed after the end of the trial.

- [REDACTED]

7.2.7.1 Methods and Timing of Sample Collection

One blood sample of 3 mL blood for prespecified pharmacogenomic testing will be obtained at Visit 2 in a potassium EDTA-anticoagulant blood drawing tube. [REDACTED] For additional information, see [Section 17.2.1, Table of Pharmacokinetic, Biomarker, and Pharmacogenomic Sampling](#) and in the Lab Manual/ISF.

The PAXgene Blood DNA tubes and EDTA containing blood sampling tubes can be stored and shipped at room temperature within 14 days. If a longer storage and shipment period for PAXgene Blood DNA tubes is necessary, these blood samples should be stored at a temperature of -20°C or below. Once frozen, thawing of the samples should be avoided.

7.2.7.2 Analytical Determinations

DNA will be extracted from blood samples according to standard molecular genetics methods and analyzed by standard genotyping and gene expression technologies.

Detailed instructions for pharmacogenomic sampling, handling and shipment of samples are provided in the Lab Manual/ISF.

7.2.8 BIOMARKERS

Measurement of biomarkers is exploratory.

[REDACTED]

After completion of the study, leftover samples may be used for further methodological and/or other, non-genetic biomarker investigations either by the sponsor, or designee. The study samples will be discarded after completion of the additional investigations, but not later than 3 years after the final study report has been archived.

7.2.8.1 Method of Sample Collection

For quantification of ALK4290 plasma concentrations (see [Section 7.2.6](#)) and for biomarker investigations, one blood sample of approximately 6 mL per sampling time point (see [Section 17.2.1, Table of Pharmacokinetic, Biomarker, and Pharmacogenomic Sampling](#) and [Section 15.1 Schedule of Events Table](#)) will be taken from an antecubital or forearm vein into a potassium EDTA-anticoagulant blood drawing tube.

The EDTA-anticoagulated blood samples will be centrifuged to collect plasma. For pharmacokinetic studies only, the obtained plasma will be split into 2 aliquots and stored in polypropylene tubes. At the selected time points with additional biomarker determinations, 5 instead of 2 aliquots of at least 0.5 mL plasma each will be prepared from the blood sample. The time from blood collection until the transfer of plasma aliquots into the freezer should not exceed 60 minutes, with interim sample storage on wet ice whenever possible. Samples will be positioned upright and will be frozen at approximately -20°C or below until shipment. These aliquots will be collected by the central laboratory. Details of plasma collection, sample handling, and shipment instructions will be given in the Lab Manual in the ISF.

7.2.8.1 Analytical Determinations

The exploratory biomarker measurements will be conducted either at the sponsor’s labs or at external CROs using appropriate methodology (e.g., immunoassays, multiplex technology). A Lab Manual/ISF will describe the handling of the samples.

8 INVESTIGATIONAL PLAN

8.1 VISIT SCHEDULE

All study agent administrations at the study site will be done under the direct supervision of the study personnel for documentation of precise administration times. In case a visit is delayed beyond the window detailed in [Section 15.1, Schedule of Events Table](#), the delayed visit should be scheduled as soon as possible and documented with the actual date and the reason for the delayed visit. The next visit, should still take place at the time it was originally scheduled in this treatment course. Any delays in visit dates, outside of the defined criteria in the Schedule of Events Table, will be reported as a protocol deviation.

8.2 VISIT PROCEDURES

The investigations as outlined in [Section 15.1, Schedule of Events Table](#) will be performed at the respective visits as described in detail in the following sections.

8.2.1 SCREENING AND RUN-IN PERIOD

The screening period (Visit 1), i.e. the phase after informed consent and before the first administration of the study agent, may be as long as 6 days (day -7 to -2). However, a pretrial fundus photography/FA examination performed within 14 days prior to Visit 1 can be used as the screening ophthalmologic examination. In special cases where it is not logistically possible to meet the protocol defined screening period, the screening can be extended by an additional 7 days (day -14) without repeating the screening assessment.

The medical history and medication history within 3 months prior to Visit 1, as well as baseline condition of the subject, will be captured in the eCRF.

8.2.1.1 Visit 1

At Visit 1, the following procedures and assessments are performed:

- Signing of all applicable Informed Consents
- Potential study subject eligibility based on all study-specific inclusion and exclusion criteria (see [Sections 5.1](#) and [5.2](#))
- Demographics and medical history
- All ophthalmological evaluations: BCVA, SD-OCT, fundus photography/FA, slit lamp, and IOP (see [Sections 7.1](#) and [7.2.5](#))
- Vital signs, physical examination, safety laboratory tests, **Poland only**: serum pregnancy test (in women of childbearing potential), and 12-lead ECG (see [Sections 7.2.2](#), [7.2.3](#) and [7.2.4](#))
- Review of concomitant medications (see [Sections 6.3](#) and [6.4](#))
- AE reporting and evaluation according to [Section 7.2.1](#)

8.2.2 TREATMENT PERIOD

All ophthalmic examinations and other assessments will be performed before intake of the study agent on the respective day. The examinations of each visit are specified in [Section 15.1, Schedule of Events Table](#). In addition, please see [Section 17.2.1, Table of Pharmacokinetic, Biomarker and Pharmacogenomic Sampling](#) for detailed information regarding these evaluations.

8.2.2.1 Visit 2

At Visit 2, the following procedures and assessments are performed:

- Pharmacokinetic and biomarker samples are taken (see [Sections 7.2.6](#) and [7.2.8](#))

- Pharmacogenomic samples are taken (see [Section 7.2.7](#))
- Specified ophthalmological assessments: BCVA, SD-OCT, slit lamp, and IOP
- Vital signs, physical examination, safety laboratory tests, and **Poland only:** serum pregnancy test (in women of childbearing potential)
- Review of concomitant medications
- AE reporting and evaluation
- Study agent administration training and study agent dispensing/administration
- Study agent accountability

8.2.2.2 Visit 3

At Visit 3, the following procedures and assessments are performed:

- Pharmacokinetic samples are taken
- Specified ophthalmological assessments: BCVA, SD-OCT, slit lamp, and IOP
- Vital signs, safety laboratory tests, and 12-lead ECG
- Review of concomitant medications
- AE reporting and evaluation
- Study agent dispensing/administration
- Study agent accountability

8.2.2.3 Visit 4

At Visit 4, the following procedures and assessments are performed:

- Pharmacokinetic samples are taken
- Specified ophthalmological assessments: BCVA, SD-OCT, slit lamp, and IOP
- Vital signs, physical examination and safety laboratory tests
- Review of concomitant medications
- AE reporting and evaluation
- Study agent dispensing/administration
- Study agent accountability

8.2.2.4 Visit 5

At Visit 5, the following procedures and assessments are performed:

- Pharmacokinetic samples are taken
- Specified ophthalmological assessments: BCVA, SD-OCT, slit lamp, and IOP
- Vital signs and safety laboratory tests
- Review of concomitant medications

- AE reporting and evaluation
- Study agent dispensing/administration
- Study agent accountability

8.2.2.5 Visit 6

At Visit 6, the following procedures and assessments are performed:

- Pharmacokinetic and biomarker samples are taken
- Specified ophthalmological assessments: BCVA, SD-OCT, slit lamp, and IOP
- Vital signs, physical examination, safety laboratory tests, and 12-lead ECG
- Review of concomitant medications
- AE reporting and evaluation
- Study agent dispensing/administration
- Study agent accountability

8.2.2.6 Visit 7

At Visit 7, the following procedures and assessments are performed:

- Pharmacokinetic samples are taken
- Specified ophthalmological assessments: BCVA, SD-OCT, slit lamp, and IOP
- Vital signs and safety laboratory tests
- Review of concomitant medications
- AE reporting and evaluation
- Study agent dispensing/administration
- Study agent accountability

8.2.3 END OF TREATMENT

All end of treatment (EOT) study-related procedures will be conducted at the conclusion of 6 weeks of treatment on Day 43 \pm 1. However, for subjects who withdraw consent from the study, no study procedures will be done thereafter. For subjects that withdraw from the study agent, EOT procedures and follow up visits are to occur as per the protocol. Excluding cases of medical emergency, but prior to the discontinuation of a subject from the clinical study for disease worsening, the study investigator should discuss each case of discontinuation with the sponsor.

8.2.3.1 Visit 8

At Visit 8, the following procedures and assessments are performed:

- Pharmacokinetic and biomarker samples are taken
- All ophthalmological assessments: BCVA, SD-OCT, fundus photography/FA, slit lamp, and IOP
- Vital signs, physical examination, safety laboratory tests, **Poland only:** serum pregnancy test (in women of childbearing potential), and 12-lead ECG
- Review of concomitant medications
- AE reporting and evaluation

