5.3 SUBJECT WITHDRAWAL OR TERMINATION

5.3.1 REASONS FOR WITHDRAWAL OR TERMINATION

A subject will be withdrawn from the study for the following medical or administrative reasons:

- Occurrence of an AE that represents an unacceptable risk to the subject and when continued participation in the investigational study is not warranted, in the judgment of the investigator, sponsor, or medical monitor. The investigator must follow the subject until the AE resolves or is stable
- Treatment with a prohibited concomitant medication other than the use of appropriate medications for the treatment of AEs under direction of the investigator
- Subject noncompliance, defined as refusal or inability to adhere to the trial schedule or procedures
- At the request of the subject or the subject’s legally authorized representative (e.g., subject withdraws consent), investigator, sponsor or regulatory authority
- Pregnancy

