5.3.2 HANDLING OF PARTICPANT WITHDRAWALS OR TERMINATION

Approximately 30 subjects will be enrolled in the study. Subjects will be encouraged to complete the study and all assessments. However, subjects may voluntarily withdraw at any time, and the investigator may discontinue individual subjects from the study at any time. For subjects who withdraw consent from the study, no study procedures will be done thereafter. For those that withdraw from receiving the study agent, follow-up visits and the safety phone follow-up are to occur as per the protocol. Excluding cases of medical emergency, but prior to the discontinuation of a subject from the clinical study for disease worsening, the study investigator should discuss each case of discontinuation with the sponsor and/or the medial monitor.

The subject withdrawal criterion below should be used to assess worsening or disease progression. In such cases, a documented assessment by the principle investigator is required, and subjects with clinically significant disease progression should be considered for withdrawal from the study and subsequent initiation of standard of care:

- A BCVA loss of ≥ 5 letters from baseline
- New macular subretinal hemorrhage
- Investigator discretion based on acute worsening of underlying disease or substantial risk to further participation in the study

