6.4 PROHIBITED TREATMENTS, MEDICATIONS, AND PROCEDURES

No other interventional therapy for wAMD is concomitantly allowed.

The use of oral corticosteroids or high potency topical steroids (e.g. with systemic exposure) are restricted during the screening and treatment period of the study. The use of inhaled corticosteroids will be allowed if stably treated for 4 weeks prior to screening without a dose adjustment and not anticipated to require a dose adjustment during the study treatment period. The use of low potency topical corticosteroids (other than those intended for ocular application) will be allowed.

Primarily, no changes in concomitant therapy will be allowed except for treatments permitted according to [Section 6.3](#) above. However, in case of adverse events in need of treatment, symptomatic therapy according to the judgement of the investigator will be permitted. All concomitant therapies and/or rescue therapies will be recorded on the appropriate pages of the eCRF.

[REDACTED] Subjects should be advised to avoid alcoholic beverages from 48 hours before study agent administration and until the end-of-study examination.

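### The protocol conflicts on whether subjects withdrawn from the study for an AE, prohibited medication or progression still attend Visit 8, so Day 43 BCVA can go missing for outcome-related reasons

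*Protocol*

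**What the plan says.** **Who keeps Visit 8.** Protocol 8.2.3 places the end-of-treatment procedures at Day 43 ±1, exempts subjects who withdraw consent, and then states: "For subjects that withdraw from the study agent, EOT procedures and follow up visits are to occur as per the protocol". Section 8.2.4 gives follow-up after Visit 8 to all dosed subjects. Its exceptions are loss to follow-up, consent withdrawal, death, and agreement between investigator and sponsor not to pursue it.

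**Who leaves the study.** Section 5.3.1 opens with "A subject will be withdrawn from the study for the following medical or administrative reasons". The list includes an AE that is an unacceptable risk, and "Treatment with a prohibited concomitant medication other than the use of appropriate medications for the treatment of AEs under direction of the investigator". For worsening, 5.3.2 says "subjects with clinically significant disease progression should be considered for withdrawal from the study and subsequent initiation of standard of care"; the criteria include "A BCVA loss of ≥ 5 letters from baseline". That step needs a documented assessment and, outside emergencies, prior discussion with the sponsor and/or medical monitor. Section 8.2.3 itself speaks of what happens "prior to the discontinuation of a subject from the clinical study for disease worsening", so it too recognises study discontinuation as a separate event.

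**What 5.3.2 keeps for agent stoppers.** "For those that withdraw from receiving the study agent, follow-up visits and the safety phone follow-up are to occur as per the protocol". Visit 8 is not named there, nor in the corresponding sentence of footnote 7 to the schedules (Protocol 15.1, SAP 4.2).

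**Rescue.** Section 6.4: "No other interventional therapy for wAMD is concomitantly allowed". The same section requires rescue therapies to be recorded in the eCRF.

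**Analysis.** SAP 14 tests the change to Visit 8 / Day 43 in the Evaluable set, which SAP 8.3 defines by three or more weeks of treatment. SAP 9.1 imputes only dates. SAP 9.3 maps Days 40 to 46 to Visit 8. The sensitivity repeat uses the Per Protocol set, which SAP 8.4 limits to study completers.

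**The concern.** Stopping the drug and leaving the study are different events, and the plan attaches Visit 8 explicitly only to the first. Several reasons for the second are linked to the outcome. A 5-letter loss is a loss on the primary endpoint. Under 7.2.1.2.5, worsening disease is recorded as an AE. Prohibited medication may be anti-VEGF given because the eye is deteriorating.

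A subject who leaves for such a reason after three weeks stays in the Evaluable set but has no value for the Day 43 t-test. The Per Protocol repeat drops the same subject, so it cannot reveal the problem. What remains at Day 43 is tilted toward eyes that held or gained vision. Protocol 2.2 says a favourable BCVA effect could provide the basis for a longer-term evaluation, so the Day 43 mean matters even though the trial is not confirmatory.

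**Working it through.** The plan states no power, SD or withdrawal rate, so there is no figure to reproduce. The check is on wording, then visit windows, then illustrative size.

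**1. The rules side by side**

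| Subject still consenting who… | Text placing them out of the study | Text that may keep Visit 8 |
|---|---|---|
| stops the agent only | none | 8.2.3, explicit |
| has an unacceptable-risk AE | 5.3.1, mandatory | 8.2.3 general Day 43 rule; 8.2.4 by implication |
| takes a prohibited medication | 5.3.1, mandatory | same |
| has significant progression | 5.3.2, to be considered | same |

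Rows two to four point both ways. The Protocol Summary names an early termination visit but gives it no timing, and no schedule column carries it.

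**2. Visit mapping**

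Take stop days 22 to 39: 39 − 22 + 1 = 18 days. The Visit 8 window is Days 40–46.
- Withdrawn with no later BCVA: every stop day is before Day 40, so 18 of 18 have no Visit 8 value.
- A termination visit on the stop day, then Days 50 and 57: none of these falls in 40–46, so again 18 of 18.
- Visit 8 kept at Day 43: 0 of 18 lack a value.

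These counts follow from the definitions. They show that only a visit near Day 43 supplies the endpoint; they say nothing about how often withdrawal occurs.

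**3. Size by arithmetic**

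One missing value is 1/25 = 4% of the planned evaluable set. If k of 25 are unobserved with true loss L and the rest average 0, the observed mean is too high by k × L / 25:
- k = 3, L = 10: 30/25 = 1.2 letters
- k = 5, L = 10: 50/25 = 2.0 letters

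For comparison, the smallest mean gain significant at two-sided 0.20 with n = 25 is t(0.90; 24) × SD/√25 = 1.318 × SD/5. That is 1.58 letters at SD 6, 2.11 at SD 8 and 2.64 at SD 10. These SDs are assumptions.

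**4. Size by simulation, all inputs assumed**

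n = 30; SD of change 6 to 10; correlation between visits 0.6; each loss of 5 or more letters at Visits 3–7 leads to withdrawal with probability 0.25 to 1.

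| True mean 0 | Chance of a significant gain |
|---|---|
| All Day 43 values observed | 9–11% |
| No Day 43 value after withdrawal | 39–92% (observed mean +1.2 to +7.0) |
| Day 43 obtained for all in the Evaluable set, unaffected by rescue | about 20–80% |

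With a true mean of −1.15 letters (Protocol 2.2's 10 letters a year, taken as linear: 10 × 42/365), the chance without Day 43 values is 13–85%, against 0.5–3.5% with complete data.

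The upper ends assume certain withdrawal at every 5-letter loss, which 5.3.2 does not prescribe. The third row stays high because the three-week rule removes subjects withdrawn at Visits 3 and 4 from the Evaluable set altogether. Retrieving Day 43 values does not bring them back.

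**The case against.** **The text already keeps Visit 8.** Section 8.2.3 exempts only consent withdrawal from its Day 43 rule, and 8.2.4 presupposes Visit 8 for all dosed subjects without listing AE, prohibited medication or progression as exceptions. This stands in large part. A reader might infer from 5.3 that the protocol omits Visit 8 for withdrawn subjects; the documents do not support that. They support both readings, and a site has no rule for choosing between them.

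**Rescue need not mean withdrawal.** Section 7.2.1.2.5 records worsening as an AE, and 5.3.1 exempts appropriate AE treatment, so standard of care may escape the prohibited-medication rule. This also stands, though 7.2.1.2.1 is less categorical about progression as an AE.

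**The losses stay visible.** BCVA is measured weekly, the t-test is run at every visit, the categorical loss table is by scheduled visit, all BCVA is listed for the ITT set, and the mixed model uses earlier visits. All true, and it tempers the concern. But the Day 43 test has no such protection, and the mixed model relies on data being missing at random.

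**Day 43 BCVA after anti-VEGF does not measure ALK4290.** Correct. Holding the visit is not enough by itself; the SAP must say how rescued subjects are handled.

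**The trial is exploratory, unpowered and tested at 0.20.** Also correct. The harm is to interpretation of the Day 43 mean, not to a confirmatory claim.

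**Conclusion.** The concern holds as a conflict in the text with a predictable analytic consequence. Sections 5.3.1 and 5.3.2 take or steer outcome-related cases out of the study. Section 8.2.3 expressly protects only agent stoppers. The primary t-test and its Per Protocol repeat both lose anyone without a BCVA in Days 40–46. If sites apply 5.3 literally, the likely direction is an upward shift in the Day 43 mean.

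The size cannot be stated, because neither the number of withdrawals nor their Day 43 values are known. The arithmetic shows only that a few missing losers could shift the mean by an amount of the same order as the significance threshold. The simulation ranges rest wholly on assumed inputs.

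A reader might also infer that a 5-letter loss forces withdrawal, or that the Day 43 result will be biased by a given amount. Neither follows: 5.3.2 asks for consideration after an assessment, and its frequency is unknown. The SAP also cites Clarification Memorandum #1, which is not available here and may settle the wording. The change is worth making, with medium confidence.

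**What to change.** **Protocol 5.3.1, 5.3.2, 8.2.3 and footnote 7 (also in SAP 4.2).** State that consenting subjects who stop for an AE, progression, or prohibited or rescue therapy discontinue treatment only. They have BCVA at the stopping visit, before any other wAMD therapy where feasible. They keep the existing Visit 8 at Day 43 ±1 (FA omitted if medically inappropriate) and the existing follow-up. Rules on when to stop or rescue stay as they are.

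**SAP 14.**
- Flag Day 43 BCVA obtained after other wAMD therapy; the eCRF already records rescue.
- Keep the planned t-test, using Day 43 values not affected by rescue.
- Add a sensitivity analysis that uses the last pre-rescue BCVA for rescued subjects. Run it in all dosed subjects as well as the Evaluable set, because the three-week rule also removes early losers.
- Report the result with post-rescue Day 43 values included as supportive.

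The t-test will still lack rescued subjects, so the sensitivity analysis carries the protection. It may lean the other way, since a value that triggers rescue is selected for being low; the two should be read together.

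**Cost.** A short amendment with IRB/IEC approval (12.2), some extra attendance by stoppers at visits already scheduled, and one or two extra tables.
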